### 10.5 Cross-over Phone Visit 2 (14 days post treatment)

Phone Visit 2 will occur at the completion of the first treatment period (day 14 following baseline). Medications will be reviewed again to ensure absence of any prohibited medications. Any possible adverse events (AE) will be assessed.

Study scales (ISI, MFIS, VAS-F, BDI, Global impression) will be self-administered by the participant with study staff oversight, as needed. Data from the wearable activity / sleep monitor will be collected. Completion of the 7-days sleep diary and scales (sQUAL and sFRESH) will be verified remotely.

Subjects will be instructed to take no study medication for one week, then to start taking the study medication (active or placebo) for Period 2.

### 10.6 Phone Visit 3 : Start of Treatment Period 2

Phone Visit 3 will occur 1 week after Phone Visit 2 (day 21 after baseline) and will mark the beginning of treatment period 2. Medications will be reviewed again to ensure stability of the MS medication regimen and absence of any prohibited medications. Any possible adverse events (AEs) will be assessed.

Subjects will be instructed to begin taking drug from the bottle marked "Period 2.". All subjects who received active medication in treatment period 1 will take placebo, and all subjects who received placebo in treatment period 1 will take active medication (10mg) while double blind.

## 10.7 Phone Visit 4

Phone Visit 4 will occur 5-7 days after Phone Visit 3 to review safety and tolerability through questioning about adverse events. BDI Q9 (suicidality risk) will be administered. Subjects with answer of 2 or 3 will be asked to discontinue study medication immediately and unscheduled visit or emergency referral will be arranged. Subjects with BDI Q9 score 0 or 1 who report no AEs on suvorexant 10 mg po QHS (or matched placebo) and who report a persistent sleep disturbance will be titrated to suvorexant 20 mg po QHS (or matched placebo) using a titration decision algorhythm. At this visit, subjects will be reminded to wear sleep monitors and to start recording sleep diaries.

### 10.8 Termination Phone Visit 5

Phone Visit 5 (final visit) will occur 2 weeks after Phone Visit 3 (day 35 after baseline). Medications will be reviewed again. Any possible AE will be assessed.

Study scales (ISI, MFIS, VAS-F, BDI, Global impression) will be self-administered by the participant with study staff oversight, as needed. Data from the wearable activity / sleep monitor will be collected. Completion of the 7-days sleep diary and scales (sQUAL and sFRESH) will be verified remotely. Patients will be instructed to stop taking study medication and place all unused study medication from Period 1 and Period 2 in the mailing envelope. They will be asked to include all study materials (surveys and diaries) in the envelope and to mail it as soon as possible.

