### 7.2 Interventions:

Study medication, to include 10-mg suvorexant and matching placebo, will be provided by Merck. The active medication will be suvorexant 10 mg every bedtime. The research pharmacist at EvergreenHealth will randomize the subject and the subject is provided active and placebo, in separate containers labeled for proper order of consumption based on study assignment. Study medication will be dispensed at randomization (Visit 2, start of Treatment Period 1) with separate pill bottles marked "Period 1, use this bottle first" and "Period 2, use this bottle after the break." An extra 6-day supply of medication will be provided for each study period to allow a window for scheduling of appointments.

Optional Drug Titration: There will be an optional titration to two pills at night (changes to suvorexant 20mg or matching placebo) after 5-7 days of each active treatment period. This will be based on a phone interview entailing answering questions about drug tolerance and whether the participant would like to escalate the dose of drug.

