Physical examination will be performed, both a general medical examination including vital signs and a neurological examination. Neurological exam will include disability rating by expanded disability status scale (EDSS) (Kurtzke 1983). Laboratory testing will include complete blood count (CBC), complete metabolic panel (CMP), with calculation of the Child-Pugh score for any subjects with liver dysfunction. Pre-menopausal women without surgical sterilization will have urine human chorionic gonadotropin (hCG) measured.

The wearable activity/sleep monitor will be dispensed at this visit to all subjects who meet eligibility criteria. This will be a FitBit™ device worn by the subjects throughout the remainder of the study. The research coordinator will oversee patient education around FitBit use. The FitBit is easy for subjects to put on and requires minimal user programming to upload data. Recorded outcomes are described below (see outcome measures). Subjects will be encouraged to wear the monitor 24-hours per day. Patients will be instructed to complete a sleep diary for seven days prior to next visit (see 11. Outcome measures).

## 10.3 Baseline Clinic Visit 2

Clinic Visit 2 will occur within 7-14 days after the screening visit. In addition to screening for eligibility, medications will be reviewed again to ensure stability of the MS medication regimen and absence of any prohibited medications.

Following confirmation of eligibility, an eligible patient will complete the baseline assessments of the insomnia severity index (ISI), modified fatigue impact scale (MFIS), Fatigue visual analogue scale (VAS-F), Global impression. The following measures will be provided for the participants to take home for use at the time of Phone Visit 2 and Phone Visit 5: Study scales (ISI, MFIS, VAS-F, BDI, Global impression). Sleep diaries will be provided for use after Phone Visit 1 and Phone Visit 3.

Following confirmation of eligibility, an eligible patient will be randomized in a 1:1 randomization scheme to receive suvorexant 10 mg qhs or placebo. Randomization will occur at the research pharmacy of EvergreenHealth using a computer-generated randomization list. The pharmacist will maintain a codebook indicating the treatment allocation of each subject. Study medication will be delivered by the research pharmacist to the research study staff from the

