research pharmacy (a separate locked room containing only research medications). The investigating physicians and research coordinator will be blinded as to treatment arm until the code is broken. The randomization code may be broken by the investigator only in a medical emergency. The reasons for such an emergency will be documented carefully. The subjects will receive 2 pill bottles, each containing identical appearing active or placebo study medication tablets, with identification known only to the research pharmacist. See Section 7.2 regarding study medication preparation and distribution.

The patient will be provided with pre-stamped and pre-addressed envelopes for return of unused study medication and study diaries at end of study.

### 10.4 Phone visit 1

Phone Visit 1 will occur 5-7 days after Clinic Visit 2 to review safety and tolerability through questioning about adverse events. BDI Q9 (suicidality risk) will be administered. Subjects with answer of 2 or 3 will be asked to discontinue study medication immediately and unscheduled visit or emergency referral will be arranged. Subjects with BDI Q9 score 0 or 1 who report no AEs on suvorexant 10 mg po QHS (or matched placebo) and who report a persistent sleep disturbance will be titrated to suvorexant 20 mg po QHS (or matched placebo) using a titration decision algorhythm. At this visit, subject will be reminded to wear sleep monitors and to start recording sleep diaries every morning.

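### A safety stop is not carried into the Period 2 instruction, early return of drug is not required, and Period 2 starts without a staff-asked suicidality question

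*Combined protocol and SAP*

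**What the plan says.** **Supply.** Section 7.2 dispenses the Period 1 and Period 2 bottles together at Visit 2. It describes the supply as "Study medication, to include 10-mg suvorexant and matching placebo" and adds that "An extra 6-day supply of medication will be provided for each study period".

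**Stopping.** Section 10.4 (Phone Visit 1) and section 10.7 (Phone Visit 4) stop study medication for a Q9 answer of 2 or 3 and arrange an unscheduled visit or emergency referral. Section 12.1 applies the same stop to a high BDI or Q9 score whenever it occurs. Section 12.3 says that an adverse event leading to discontinuation is followed until it resolves, where possible. It says nothing about later drug.

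**Starting Period 2.** At Phone Visit 2, section 10.5 tells subjects to pause for a week, "then to start taking the study medication (active or placebo) for Period 2". Section 10.6 repeats the start instruction at Phone Visit 3 ("Subjects will be instructed to begin taking drug from the bottle marked" Period 2) and says that "all subjects who received placebo in treatment period 1 will take active medication (10mg) while double blind". Neither section mentions a subject who has already been stopped.

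**Checks.** The scales, including the BDI, go home at baseline ("take home for use at the time of Phone Visit 2 and Phone Visit 5"). At Phone Visit 2 they "will be self-administered by the participant with study staff oversight, as needed". The Schedule of Events places Q9 at Phone Visits 1 and 4 only. Phone Visit 3 has a medication review and an adverse-event review.

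**Return.** Section 10.3 supplies "envelopes for return of unused study medication and study diaries at end of study". Section 10.8 has leftovers from both periods mailed after the final call. The contents listed for an unscheduled visit in section 10.9 do not include collecting drug.

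**The concern.** Section 12.1 treats a Q9 answer of 2 or 3 as marking serious suicide risk, and gives the drug's CNS-depressant action as the reason for monitoring. Three things should therefore follow plainly from a stop: no more drug, no stock left at home, and a direct check before any later exposure. The protocol settles the first only by inference, leaves the second to the end of the study, and makes the third depend on a self-completed form.

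For a subject on placebo in Period 1, the Period 2 bottle is the first exposure to active drug. For a stop caused by some other adverse event, there is not even an inferred rule, so sites could act differently.

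A secondary issue is the section 8.2 criterion of Q9 above 1, which is worded to apply throughout the study. It could be read as removing a randomized subject. If a site read it that way, the later ISI values would be lost although an intention-to-treat analysis is planned.

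**Working it through.** **1. Does the text stop Period 2 drug?**

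| Reason for stop | Text that stops drug | Does it reach Period 2? |
|---|---|---|
| Q9 of 2 or 3, or high BDI | 10.4, 10.7, 12.1; criterion in 8.2 | By inference: 7.2 uses study medication for active and placebo together. Not repeated in 10.5 or 10.6 |
| Other adverse event | 12.3 (follow-up of the event only) | No rule found |

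**2. How long could both bottles stay at home?** Inputs from sections 10.4-10.8, counted from baseline: Phone Visit 1 at day 5-7, Phone Visit 2 at day 14, Phone Visit 3 at day 21, Phone Visit 4 5-7 days after that, Phone Visit 5 at day 35. If drug goes back only at day 35:
- Stop at Phone Visit 1: 35 - 7 = 28 to 35 - 5 = 30 days.
- Stop at Phone Visit 2: 35 - 14 = 21 days.

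Time in the mail would add to these.

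**3. How much supply is that?** Tablet counts are not stated, so I count nights and assume each bottle covers 14 + 6 = 20. At a Phone Visit 1 stop, the Period 1 bottle has 20 - 7 = 13 to 20 - 5 = 15 nights left, and the Period 2 bottle has all 20. One of the two bottles is active.

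**4. How long between suicidality checks?** After the day-14 BDI, the next Q9 is at Phone Visit 4: day 21 + 5 = 26 to day 21 + 7 = 28. The gap is 26 - 14 = 12 to 28 - 14 = 14 days. Seven of these are washout, and the last 5-7 are on Period 2 drug.

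**5. What would keeping stopped subjects in the ITT analysis cost?** This prices the fix and has no bearing on how serious the gap is. Inputs from section 13: difference 1.75, SD of the difference 4.1, two-sided 5%, 50 enrolled, 45 analysed.
- The plan's 81% reproduces closely: Phi(1.75/4.1 x sqrt(45) - 1.96) = 0.817, or 0.800 by paired t.
- Assume that k stopped subjects show no treatment difference and all others complete. Keeping them gives a mean difference of 1.75(50 - k)/50, a fall of 0.035 points (2%) per subject.

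| k | Mean if kept | Paired-t power, kept (n = 50) | Paired-t power, removed (n = 50 - k) |
|---|---|---|---|
| 1 | 1.715 | 82.6% | 83.3% |
| 2 | 1.680 | 81.1% | 82.5% |
| 5 | 1.575 | 75.9% | 80.0% |

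The last row is an extreme: it makes the plan's whole 10% loss allowance safety stops.

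**The case against.** The strongest reply is that the main case is already governed. Section 12.1 stops drug after a high score at any time, section 7.2 uses study medication for both products, and section 8.2 makes a Q9 above 1 disqualifying throughout. On this view sections 10.5 and 10.6 simply describe the ordinary visit flow. That largely stands. A reader might infer that the protocol orders Period 2 drug for a subject at suicide risk, but the documents do not support this, because the visit sections are silent on stopped subjects and do not override section 12.1. For Q9 and BDI stops, the missing exception is mostly a clarification.

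The reply also has force on retention. No passage says that a stopped subject keeps both bottles. That is inferred from the single return route. Envelopes are in hand from baseline, and staff could collect drug at the unscheduled visit. What stands against it is that nothing requires either.

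A reader might also infer that the Phone Visit 2 BDI goes unread until the forms are mailed. Section 12.1 says the BDI is administered at that visit and requires immediate action on a high score, so it implies a prompt reading. The narrower point remains: no passage says the score is read on the call before the Period 2 instruction is given.

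Nothing in the reply supplies a rule for Period 2 after an adverse-event stop.

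**Conclusion.** The concern holds as a safety gap that is cheap to close. Three parts are firm: there is no Period 2 rule after an adverse-event stop, there is no stated early return of drug, and no Q9 is asked at Phone Visit 3. The missing exception for Q9 and BDI stops is a lesser matter of making an implied rule explicit.

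The size is 28-30 days of possible retention after a Phone Visit 1 stop and 21 days after a Phone Visit 2 stop, assuming that the end-of-study return is followed as written and nobody collects drug earlier. The number of subjects affected is unknown. It is probably low, since screening excludes a BDI above 28 or a Q9 above 1.

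The endpoint issue is secondary and conditional. A reader might infer that section 8.2 takes stopped subjects out of the ITT analysis, but no passage says so, and the scales at Phone Visits 2 and 5 do not depend on being on drug. For a given subject, removal under section 8.2 and receipt of Period 2 drug are alternatives, so the two harms do not add. The primary analysis is not threatened.

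**What to change.** 1. In sections 10.5 and 10.6, except any subject stopped for safety. A Q9 or BDI stop permanently bars drug from both bottles. An adverse-event stop bars Period 2 drug unless the investigator clears it and documents the reason; add this rule to section 12.3.
2. In sections 10.4, 10.7, 10.9 and 12.1, require all unused drug back at the time of the stop: at the unscheduled visit, otherwise in the pre-stamped envelope already supplied.
3. Have staff ask Q9 on the calls at Phone Visits 2 and 3, before giving the Period 2 instruction.
4. Secondary: state in section 8.2 that a Q9 above 1 after randomization stops drug but does not remove the subject. Unless consent is withdrawn, still collect the scheduled scales at Phone Visits 2 and 5, record the stop date, and include the values in the ITT analysis (section 13).

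The cost is wording, one spoken question on two calls already scheduled, and one early bottle return per stopped subject. The scales are already in the subject's home. Off-drug values dilute the ITT estimate slightly: 0.7 points of power for one stopped subject (83.3% - 82.6%) and 1.4 for two (82.5% - 81.1%), on the assumptions above. No change in sample size follows.

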#### **12.2 Adverse Events**

Subjects will be monitored for adverse events throughout the trial. The occurrence of adverse events will be ascertained by observation, telephone monitoring and questioning by the investigator. Safety assessments will consist of monitoring and recording all adverse events, including serious adverse events.

An AE is any symptom, physical sign, or medical condition that emerges during the study or, if present at screening, worsens during the study, regardless of the suspected cause. Adverse events include adverse drug reactions, illness with onset during the study, exacerbations of pre-existing conditions or clinically significant changes in physical examination or significantly abnormal objective test findings. Medical conditions/diseases present before starting study treatment are only considered adverse events if they worsen after starting study treatment. All adverse events will be recorded and graded as mild, moderate or severe by the principal investigator in accordance with general guidelines of clinical research, outlined here:

- MILD: An event that causes transient or minimal symptoms and that does not interfere with daily activities.
- MODERATE: An event that causes symptoms sufficient to interfere with but not prevent daily activities.
- SEVERE: An event that prevents normal, everyday activities.

Adverse events will also be classified by their relationship to the study medication by the principal investigator in accordance with general guidelines of clinical research, outlined here:

- Unrelated: There is no reasonable association between the study treatment and the suspected event and the event could have been produced by the patient's clinical state or other therapy administered to the patient.
- Possibly related: The suspected AE may or may not follow a reasonable temporal sequence from study treatment administration but seems to be the type of reaction that cannot be dismissed as unlikely. The event could have been produced or mimicked by the patient's clinical state or other therapy administered to the patient.
- Probably related: The suspected AE follows a reasonable temporal sequence from study treatment administration, abates upon discontinuation of the treatment, and cannot be reasonably explained by the known characteristics of the patient's clinical state or other treatments.

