#### **12.3 Serious Adverse Events**

A serious adverse event (SAE) is any AE that meets one of more of the following criteria:

- Is fatal or life-threatening
- Requires hospitalization or prolongs a current hospitalization
- Results in persistent or significant disability/incapacity
- Is a congenital anomaly
- Requires medical or surgical intervention to prevent one of the above outcomes

If any SAE occurs, the treatment status of the subject(s) may be revealed, as clinically indicated. If a patient discontinues medication use due to an AE, the event will be followed, when possible, until resolution. No interim analysis of safety data is planned because the entire study will be conducted over 2 months. However, the frequency of AEs will be under continuous scrutiny during the trial with comparison to AE rates that have been recorded in published PD drug trials.

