# 13. Data Management and Statistical Analysis

#### **Sample Size Considerations**

This is a prospective, double-blinded, randomized controlled pilot study. The purpose is to test a hypothesis in a preliminary fashion in this population with a specific neurological disease. In our initial statistical plan, the study was underpowered, based on an enrollment target of 30 subjects. We later increased the enrollment to 50 subjects to adequately power the study. We assume that no more than 10% of subjects will withdraw, be lost to follow-up or be dropped for protocol violations, leaving 45 subjects for final analysis. Power calculation is based on a cross-over design. We assume that the true difference in mean Insomnia Severity Index (ISI) between the treatments will be 1.75 units based on the findings of a cross-over trial by Herring et al for treatment effect of suvorexant on ISI in patients with primary insomnia. (Herring et al, 2012) We assume that our cohort with MS with adjustable dose titration (10mg and 20mg) will yield a slightly lower treatment response than that of the Herring cohort at 20mg (-2.0 units). We assume a normal distribution with standard deviation of the difference in the ISI is 4.1, based on normative data from Bastien, et al, who conducted the primary validation study. (Bastien et al, 2001) With these assumptions, the probability (power) is 81 percent that the study will detect a treatment difference at a two-sided 5.000 percent significance level. (PS Power and Sample Size Calculations, version 1.7.15, http://hedwig.mgh.harvard.edu/sample\_size/size.html#cross)

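### The last planned adverse event check is the call that stops Period 2 drug, so an event ongoing at day 35 cannot be graded above possibly related from planned contacts

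*Combined protocol and SAP*

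**What the plan says.** Section 10.8 fixes the end of the study: "Phone Visit 5 (final visit) will occur 2 weeks after Phone Visit 3 (day 35 after baseline"). AEs are assessed at that call, and the stop instruction is given during it: "Patients will be instructed to stop taking study medication and place all unused study medication". In the Schedule of Events the only column after Phone Visit 5 is the one for unscheduled visits.

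Period 1 ends differently. At Phone Visit 2 (section 10.5), "Subjects will be instructed to take no study medication for one week", and AEs are asked about again at Phone Visit 3 on day 21 (section 10.6), before Period 2 drug is started.

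Section 12.2 has four relatedness grades. Probably related requires, among other things, that the event "abates upon discontinuation of the treatment, and cannot be reasonably explained" by the patient's condition or other treatments. Definitely related carries the same requirement that the event subside off drug and, where appropriate, adds recurrence when drug is given again. Possibly related has no such requirement.

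The only stated rule for following an event over time is in section 12.3: "If a patient discontinues medication use due to an AE, the event will be followed, when possible, until resolution". Section 10.9 allows subjects to come back for a safety evaluation as needed.

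**The concern.** The protocol defines its two higher causality grades by an observation made after drug is stopped. Its schedule supplies that observation after Period 1 but not after Period 2. Two kinds of information are lost.

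- **Causality.** An event present at day 14 can be checked at day 21 and upgraded if it has gone. The same event present at day 35 has no later planned contact, so on planned data its grade stops at possibly related.
- **Events that begin after stopping.** For subjects who take suvorexant second, no planned contact asks about them. Section 5 says only that absence of rebound insomnia is believed, and that people with MS may be more sensitive to the drug's adverse effects. A pilot in this population would be expected to look for such events in everyone exposed.

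**Working it through.** This point rests on the visit calendar and the grade definitions, not on the power calculation.

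**Step 1: the calendar.** Inputs are 2 weeks of treatment, 1 week of washout and 2 weeks of treatment (section 7.1). 14 + 7 = day 21 and 21 + 14 = day 35, which match sections 10.6 and 10.8. Phone Visit 4 falls 5 to 7 days after day 21, so on days 26 to 28.

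| AE contact | Day | Suvorexant first | Suvorexant second |
|---|---|---|---|
| Phone Visit 1 | 5–7 | on suvorexant | on placebo |
| Phone Visit 2 | 14 | end of suvorexant | end of placebo |
| Phone Visit 3 | 21 | 7 days off all study drug | 7 days off all study drug |
| Phone Visit 4 | 26–28 | on placebo | on suvorexant |
| Phone Visit 5 | 35 | end of placebo | end of suvorexant |
| Later | – | none planned | none planned |

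A late Phone Visit 5 need not create an off-drug gap before the call, because section 7.2 supplies 6 extra days of medication per period to allow for scheduling.

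**Step 2: how many subjects.** Section 10.3 says "an eligible patient will be randomized in a 1:1 randomization scheme to receive suvorexant 10 mg qhs or placebo", and section 10.6 says "all subjects who received placebo in treatment period 1 will take active medication (10mg) while double blind". The enrolment target is 50: "We later increased the enrollment to 50 subjects to adequately power the study". So 50 × 1/2 = 25 subjects take suvorexant second. With the 45 expected for final analysis, 45 × 1/2 = 22.5, or 22 to 23. These are approximate, since no blocking is described.

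**Step 3: untreated time after suvorexant that ends in a planned AE check.**

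- Suvorexant first: 25 × 7 = 175 subject-days.
- Suvorexant second: 25 × 0 = 0 subject-days.

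**Step 4: the grade that planned contacts can support.**

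- Ongoing at day 14, gone by day 21: the off-drug requirement is met, so the higher grades are open if their other conditions hold.
- Ongoing at day 35: no planned contact can show whether it subsided, so the highest supportable grade is possibly related. This holds whichever treatment was taken in Period 2.

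**Step 5: what following half the subjects means for post-stop events.** The documents give no rate, so the rates below are assumptions. With k subjects followed, and every event detected at the contact, P(at least one) = 1 − (1 − p)^k.

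| Assumed rate p | k = 25 | k = 50 |
|---|---|---|
| 1% | 22% | 39% |
| 2% | 40% | 64% |
| 5% | 72% | 92% |
| 10% | 93% | 99% |

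If no such event is seen, the one-sided 95% upper bound on the rate is 1 − 0.05^(1/k): 11.3% with 25 subjects and 5.8% with 50.

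**The case against.** The best reply is that the gap is only partial and has little consequence. Much of this stands, and it rules out four stronger readings.

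- **No off-drug follow-up of any kind.** A reader might infer this, but the documents do not support it. A subject who stops early because of an AE is followed under section 12.3, and may already be off drug at Phone Visit 5. Section 10.9 offers as-needed visits with a review of adverse effects. The correct wording is no *planned* contact. These routes do not close the gap, however: reaching the scheduled end at day 35 is not stopping because of an AE, unscheduled visits happen only as needed, and the protocol does not say whether they remain available after the final visit.
- **A suicidality signal at the end of Period 2 goes unanswered.** It does not. The full Beck inventory is given at Phone Visit 5, and section 12.1 provides for an unscheduled visit or emergency room referral after a high total or question 9 score at any point. Only ideation that first appears after that call lacks a planned contact.
- **A contrast of 21 days against 0.** Days 21 to 35 in the suvorexant-first sequence are spent on blinded Period 2 tablets, so a blinded grader cannot treat them as known off-drug time. The fair contrast is 7 days with one check against 0.
- **A bias between suvorexant and placebo.** The grade limit applies to every event ongoing at day 35, including placebo events in the suvorexant-first sequence. Grading is blinded (section 12.2), and each treatment occupies Period 2 in about half the subjects. The limit goes with the period, not with the drug.

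It is also fair to say that section 13 plans no analysis by relatedness grade, and that section 12.4 triggers FDA reporting at possibly related, so the limit does not block that reporting. Exposure is short and the ISI analysis is untouched. These points bear on priority; they do not supply the missing observation.

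**Conclusion.** The point holds as a mismatch between the visit schedule and the protocol's own causality definitions. About 25 of 50 subjects have no planned AE contact off drug after suvorexant. In either sequence, an event ongoing at day 35 cannot be graded above possibly related from planned contacts. What is lost is causality and post-stop safety information for Period 2. A distorted treatment comparison is not shown, and efficacy is unaffected.

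The conclusion assumes that subjects complete Period 2 and that the 1:1 allocation splits roughly evenly. The documents do not allow an estimate of how many events will be ongoing at day 35, so the number of affected grades is unknown. The correction is worth making because it is cheap and specific.

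**What to change.** Reconcile the Schedule of Events and section 10.8 with the grade definitions in section 12.2 and the follow-up rule in section 12.3:

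1. Add one off-drug AE telephone contact after Phone Visit 5, and enter it in the Schedule of Events. The sponsor should set the interval and state its reason; the protocol's own washout of 7 days is one reference point.
2. Extend the follow-up wording in section 12.3 to events still ongoing at Phone Visit 5, and say whether unscheduled visits under section 10.9 remain available after that call.
3. Assign final relatedness grades after the new contact and before unblinding, so that events from both periods are judged on off-drug information.

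The cost is a protocol amendment, one short call by existing staff and one further visit stipend for each of up to 50 subjects, and slightly longer participation off drug. No extra medication or clinic visit is needed.
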